5.9.3. Subgroup Analyses

The following sub-groups will be examined for the primary endpoints. Results will be displayed in both tabular form and graphical form using a forest plot.

- Age (≤ 65 vs > 65)
- Gender (male vs female)
- Remdesivir Use within 24 hours of Randomization (yes vs no)
- Country (USA, Brazil)
- Corticosteroid Use (e.g., Dexamethasone) (yes vs no)
- Patients with a positive PCR test at baseline vs not positive.
- Patients with IL-6 $>$ median at baseline vs \leq median

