
 Additional efficacy outcomes 	
 Mortality rate during the 28-day study period following enrollment Time to hospital discharge readiness Proportion of subjects ready to be discharged from the hospital during the 28-day study period following enrollment Proportion of subjects with resolution of fever below entry criteria for 24 hours (as defined in Section 5.1.1) by Day 10 in subjects with fever at baseline Time to resolution of fever below entry criteria for 24 hours (as defined in Section 5.1.1) in subjects with fever at baseline Duration (in days) of remdesivir use in subjects starting remdesivir within 24 hours of first dose of BLD-2660 Change from baseline to Days 10, 14, 21 and 28 in clinical status outcome using a 6-point ordinal scale (Section 8.1.3) Proportion of subjects reporting each 6-point ordinal scale of the clinical status outcome assessment Change from baseline to Days 5, 10, 14, 21 and 28 in NEWS score Change from baseline to Days 10, 14, 21 and 28 in IL-6 and D-dimer
Exploratory	

 Other efficacy outcomes 	
 Proportion of subjects who require mechanical ventilation after study entry Number of ventilator-free days to Day 21 Proportion of subjects with ICU transfer and/or ventilator dependence during the 28-day study period following enrollment

Objectives	Endpoints
	
 • The time to a NEWS of ≤ 2 and maintained for 24 hours • Change in NEWS from baseline to Days 3, 5, 8, 10, 14, 21 and 28 in NEWS

 • To evaluate antiviral activity of BLD-2660 in the same population 	
 • Proportion of subjects who are SARS--CoV-2 virus free by Day 10/EOT or hospital discharge, whichever is sooner • Time to eradication of SARS-CoV-2 • Change from baseline in SARS-CoV-2 viral load at Days 5, 10, 14, and 28

 • Other safety outcomes 	
 • Clinically relevant changes from baseline in electrocardiogram (ECG), and clinical laboratory values at each post baseline timepoint • Proportion of subjects with clinically significant drug-related troponin elevations that have repeat elevation upon confirmatory testing as adjudicated by the DMC while continuing on study drug during the 10-day treatment period

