6.4. Measures to Minimize Bias: Randomization and Blinding

All subjects will be centrally assigned to randomized study drug using an Interactive Response Technology (IRT). Before the study is initiated, the log in information & directions for the IRT will be provided to each site.

Randomization will be stratified by remdesivir use at study entry (yes/no)

Study drug will be dispensed by the unblinded pharmacy staff to the study staff/research nurse in a blinded manner per the schedule summarized in the SoA ([Section 1.2](#)).

The IRT will be programmed with blind-breaking instructions. Subject safety must always be the first consideration in making such a determination. If the Investigator decides that unblinding is warranted, the Investigator should make every effort to contact the Sponsor prior to unblinding a subject's drug assignment unless this could delay emergency treatment of the subject. If a subject's drug assignment is unblinded, the Sponsor must be notified within 24 hours after breaking the blind. The date and reason that the blind was broken must be recorded in the source documentation and case report form, as applicable.

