6.6. Concomitant Therapy

All medications including over-the-counter medications and herbal supplements taken during the 30 days prior to the first study drug administration will be recorded and reviewed by the Investigator (or designee) to determine whether the subject is eligible for inclusion.

Treatment with another study drug, investigational device, or approved therapy for investigational use within 30 days (or five half-lives, whichever is longer) before anticipated dosing is prohibited.

Allowed medications during the study:

- Remdesivir

Note, for subjects receiving remdesivir therapy, BLD-2660 is to be administered at least an hour before remdesivir administration.

6.6.1. Prohibited Medications and Herbal Supplements:

Below is a list of medications that are prohibited **during the study**.

- Anti-IL-6, IL-6 receptor antagonists, or JAKi

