1.2. Study Design

This is a Phase 2 randomized, double-blind, placebo-controlled multicenter study designed to evaluate BLD-2660 as add-on to standard of care (SOC) therapy in hospitalized participants with recently diagnosed COVID-19 compared to SOC treatment.

The study will include a Screening period, a Treatment period, and a Follow-up period.

After signing informed consent form (ICF), potential candidates who are hospitalized for confirmed infection with SARS-CoV-2 will undergo additional screening procedures.

On Day 1, eligible participants will be randomized in 2:1 ratio to one of 2 treatment groups, active or control, as shown in Table 1. Randomization will be stratified by remdesivir at study entry. All participants will receive study drug in combination with SOC over 10 days (through Day 10/end of treatment) or until hospital discharge, if sooner. Participants will be followed for at least 18 days after the last dose of study drug on Days 14, 21 and 28. Participants will be contacted 60 days post-study to collect information on mortality and forced vital capacity (FVC).

CONFIDENTIAL

Statistical Analysis Plan [Version 3.0]

Table 1: Treatment Groups

Treatment Group	Dose Level, Schedule and Route of administration	Number of participants
Active	BLD-2660 900 mg twice per day (BID), oral + SOC	80
Control	Matching placebo, BID, oral + SOC	40

For each participant, the study duration for each study period is expected to last as follows:

Study Period	Duration
Screening period	Up to 3 days
Treatment period	10 days
Treatment Follow-up period	18 days
Post study follow-up period	32 days

Interim analyses are planned when approximately 25%, 50% and 75% of participants have completed the study for the purpose of reviewing safety data and for the purpose of early stopping for efficacy or futility. At the 50% interim analyses, the sample size may be increased.

The final analysis will occur once the last participant enrolled completes the end of study follow-up visit. Data from the post study follow-up visit regarding FVC will be included in the final databased after the final analysis has been completed.

2. Statistical Hypotheses

Two primary statistical hypotheses will be tested. The study will be declared a success if either of the hypotheses are statistically significant. As this is a phase 2 study, no adjustment for multiplicity will be made for having two co-primary hypotheses.

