5.5.2. Main Analytical Approach

Time to Clinical Improvement

Time to clinical improvement will be presented by treatment group, using the Kaplan-Meier estimator. A Cox proportional hazards model with treatment, remdesivir strata (yes/no) and age (years) as covariates will be used to estimate the hazard ratio and compare treatment groups. Additional covariate's (i.e., Country (USA, Brazil), Chloroquine or hydroxychloroquine use (yes vs no), HIV anti-viral drug use (yes vs no), corticosteroid use (yes vs no) and azithromycin use (yes vs no)) may also be included if these are found to influence the treatment effect, based on observing p-value of < 0.05 for the covariate, after adjusting for the others in the model. The

stepwise selection procedure will be used to assess the additional covariates. In addition, the log rank test and stratified log rank test, with remdesivir as the strata, will be provided. The primary analysis will be conducted using the FAS.

Change from baseline to Day 10 or hospital discharge if sooner, in the ratio of hemoglobin oxygen saturation to inspired oxygen fraction (SpO₂/FiO₂)

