The primary efficacy endpoint of change from baseline to Day 10 or hospital discharge if sooner, in the ratio of hemoglobin oxygen saturation to inspired oxygen fraction (SpO₂/FiO₂) will be analyzed using a mixed model for repeated measures (MMRM). The Kenward-Roger method will be used to calculate the denominator degrees of freedom for the test of fixed effects and adjusted standard errors. The model will contain treatment, time and the treatment by time interaction as fixed effects and baseline score, age (years), corticosteroid use (yes vs no) and remdesivir strata as covariates. If age and/or corticosteroid use are not significant at the 5% level, they will be removed from the model. As the follow-up visit schedule for each participant will be variable, the following timepoints will be used; Day 1, Day 2, Day 3, Day 4, Day 5 and Day 10/Discharge. Additional time points (e.g., Days 6-9) may be included if most participants are not discharged prior to Day 10. An unstructured covariance matrix will be assumed to model the within-participant errors. This variance-covariance matrix will be estimated across treatment groups. However, if there is a convergence problem with the unstructured covariance matrix, then alternative covariance structures will be examined (heterogeneous Toeplitz structure, Compound Symmetry) and the one with the best fit as determined by the Akaike information criteria (AIC) (i.e., smallest AIC value) will be used. The least squares means (LS-means) for each treatment, LS-means treatment difference and corresponding confidence interval (CI) for the LS-means difference and p-value for the treatment difference, will be reported at the Day10/Discharge timepoint.

The primary analysis will be conducted using the FAS.

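### The remdesivir subgroup uses a 24-hour window around randomization instead of the randomization stratum, so patients who start remdesivir in the first 24 hours after randomization can change group

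*SAP*

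**What the plan says.** Remdesivir use is the only stratification factor. Protocol 6.4 states: "Randomization will be stratified by remdesivir use at study entry (yes/no"). SAP 1.2 agrees: "Randomization will be stratified by remdesivir at study entry".

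Both primary models in SAP 5.5.2 carry that stratum. For time to clinical improvement the plan is "A Cox proportional hazards model with treatment, remdesivir strata (yes/no) and age (years) as covariates", with a log-rank test stratified by remdesivir alongside. The repeated-measures model for SpO2/FiO2 includes "baseline score, age (years), corticosteroid use (yes vs no) and remdesivir strata as covariates".

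The subgroup section, SAP 5.9.3, opens with "The following sub-groups will be examined for the primary endpoints" and plans tables and a forest plot. Its remdesivir row is "Remdesivir Use within 24 hours of Randomization (yes vs no"). It does not mention the stratum, does not say whether the window runs before randomization, after it or both, and gives no reason for a definition different from that in the models.

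Remdesivir is allowed during the study. Protocol 6.6 adds: "Note, for subjects receiving remdesivir therapy, BLD-2660 is to be administered at least an hour before remdesivir administration". The Schedule of Activities places both randomization and the first study drug administration on Day 1.

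**The concern.** A subgroup fixed before randomization keeps the randomized comparison intact within each of its levels. A subgroup that can be entered afterwards does not have that protection. Read in the ordinary way, a window within 24 hours of randomization covers time on both sides, and the later side includes time on study drug. If study drug changes how a patient does on the first day, and that influences whether remdesivir is started, membership becomes partly an outcome.

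There is also a plain inconsistency. The same patient can sit on different sides of the remdesivir split in the primary model and in the forest plot. The 'yes' subgroup would then mix two strata, and the SAP does not say how the remdesivir covariate is handled when the model is fitted inside it. If the subgroup were the stratum, the covariate would be constant and would simply drop out.

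At stake is how the remdesivir row of the forest plot is read for the two primary endpoints.

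**Working it through.** **1. The plan's own figures, for context.** The subgroup has no stated figure. The overall design figures reproduce:
- Time to improvement (75 events, hazard ratio 0.5, 2:1 allocation, two-sided 5%): √(75 × 1/3 × 2/3) × |ln 0.5| − 1.96 = 4.082 × 0.693 − 1.96 = 0.87. Power is 0.808, against the stated 80% or more.
- SpO2/FiO2 (difference 25, SD 40, 80 versus 40): 25 / (40 × √(1/80 + 1/40)) − 1.96 = 3.23 − 1.96 = 1.27. Power is 0.898, against the stated 90% or so.

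Redefining the subgroup changes neither figure.

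**2. One patient under each definition.** Take a patient not on remdesivir at entry, randomized and dosed on Day 1, who starts remdesivir 12 hours later.

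| Place | Rule | Group |
|---|---|---|
| Protocol 6.4, SAP 1.2 | use at study entry | no |
| SAP 5.5.2, both primary models | stratum | no |
| SAP 5.9.3, two-sided reading | use within 24 hours of randomization | yes |

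Under the Protocol 6.6 dosing order, such a patient would normally have had study drug first. A patient who starts on Day 3 stays 'no' throughout.

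**3. How many could move.** The documents give neither stratum sizes nor start rates, so both are assumptions: 40% to 80% of the 120 patients in the 'no' stratum, and 5% to 30% of those starting within 24 hours after randomization. It is also assumed that use at entry always counts as use inside the window.
- Movers = 120 × share in 'no' stratum × start rate.
- Low: 120 × 0.40 × 0.05 = 2.4. Share of the 'yes' subgroup: 2.4 / (72 + 2.4) = 3%.
- Middle: 120 × 0.60 × 0.10 = 7.2. Share: 7.2 / (48 + 7.2) = 13%.
- High: 120 × 0.80 × 0.30 = 28.8. Share: 28.8 / (24 + 28.8) = 55%.

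**4. When moving patients biases the comparison.** An illustrative simulation used 2,000,000 patients, 2:1 allocation, 40% in the 'yes' stratum, total SD 40 and no true treatment effect. Sicker patients had worse SpO2/FiO2 change and started remdesivir more often, and the control start rate was 20%. Only the active start rate was varied. Entries are active minus control, in SpO2/FiO2 units.

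| Start rate, active vs control | Window 'yes' | Window 'no' |
|---|---|---|
| 20% vs 20% | 0.0 | 0.0 |
| 14% vs 20% | +0.7 | −1.6 |
| 10% vs 20% | +1.9 | −3.0 |
| 4% vs 20% | +3.6 | −4.5 |

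Subgroups defined by stratum stayed within 0.2 of zero in every row.

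**5. Scale.** With 40% of 120 in the 'yes' stratum (32 active, 16 control) and SD 40, the standard error of a subgroup difference is 40 × √(1/32 + 1/16) = 12.2. For the 'no' stratum (48 and 24) it is 40 × √(1/48 + 1/24) = 10.0. Even the most extreme row is under half a standard error (4.5 / 10.0 = 0.45) and 18% of the design difference (4.5 / 25). The simulation covers SpO2/FiO2 only; no size was estimated for time to clinical improvement.

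**The case against.** The best defence is that nothing here is shown to be a post-randomization subgroup. Neither document defines study entry in hours, so the 24-hour phrase may be the SAP's working version of it, or may mean the 24 hours before randomization. That is possible, but neither document says so. If it is what was meant, the SAP should state it.

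The second defence is size. Study drug would have to change who starts remdesivir within about a day, in a double-blind trial, and this is one of seven subgroup rows with no test or decision rule attached. This stands, and it limits the weight of the point.

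Several stronger readings are tempting and are not supported:
- *Everyone who starts remdesivir after randomization changes group.* Only starts in the first 24 hours do.
- *The 2:1 balance is lost.* If early starts are unrelated to arm, the expected ratio holds. It is no longer guaranteed, which is a weaker statement.
- *The protocol adds a third, conflicting anchor.* Protocol 3 has the endpoint "Duration (in days) of remdesivir use in subjects starting remdesivir within 24 hours of first dose of BLD-2660", and read literally its anchor does not exist for placebo patients. But the current SAP no longer lists that endpoint and states that the SAP prevails. The protocol also uses the drug name loosely for blinded study drug (Protocol 6.5). The endpoint shows only that starts around the first dose were foreseen.
- *This subgroup is the key background-therapy question for Phase 3.* SAP 5.10 describes Phase 3 planning without mentioning remdesivir.

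**Conclusion.** The mismatch is real and worth correcting. The SAP subgroup rule differs from the stratification factor and from both primary models, and as worded it lets early post-randomization events determine membership.

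The consequence is confined to interpreting the remdesivir row of the forest plot. A reader might infer that the primary results are compromised; they are not, because both primary models use the stratum.

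The number of patients who would move cannot be computed from the documents. The range of about 2 to 29 rests entirely on assumed stratum sizes and start rates. Bias is zero in the simulation when start rates are equal in the two arms, and modest against sampling error when they differ. Given blinding and the short window, it is likely small. The case for change rests on a clear inconsistency that costs almost nothing to remove, not on a demonstrated large bias.

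**What to change.** In SAP 5.9.3, replace the 24-hour definition with the remdesivir randomization stratum: use at study entry, as recorded in the interactive response system. In the concomitant medication summaries (SAP 5.9.6), add a descriptive count by arm of patients who started remdesivir after randomization. If a 24-hour version is still wanted, label it supplementary and state whether the window runs before randomization, after it or both.

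The cost is one line in the SAP and one descriptive row. The stratum is already held in the randomization system and used in the primary models, so no new data are needed and no design figure changes. While the list is open, note that its corticosteroid row has no time window at all and is exposed to the same problem.

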5.9.4. Demographics and Baseline Characteristics

Demographic and baseline characteristics will be summarized by treatment group for the FAS set, by treatment group and overall, using descriptive statistics. No statistical hypothesis tests will be performed.

5.9.5. Medical History

Medical history will be coded using the Medical Dictionary for Regulatory Activities (MedDRA) and summarized by system organ class (SOC) and preferred term for each treatment group, and overall. At each level of summarization, a participant is counted once if he/she reported one or more medical history terms at that level. No statistical hypothesis tests will be performed.

5.9.6. Concomitant Medications

Concomitant medications are those that are taken at any time after the first dose of study medication.

If the start day of a medication is missing, then if the month and year of the start date are on or after the date of randomization, the following rules will be applied:

- If month/year of the start date is equal or after the month/year of the date of randomization, the medication will be considered concomitant;
- If month/year of the start date is equal to the month/year of the date of randomization, and the end date is present, the end date will be used to determine if the medication stopped prior to randomization or after. If the end date is after, the medication will be considered concomitant; otherwise, if the medication stopped prior, then it will be considered to be prior;
- If month/year of the start date is equal to the month/year of the date of randomization, and the end date is a partial date, the medication will be considered concomitant;
- If, despite implementing the above conventions, the start date of the medication cannot be placed before, on, or after randomization, then the medication will be considered concomitant.

Concomitant medications will be coded using the World Health Organization (WHO) Drug Dictionary and summarized by drug class (ATC Level 3) and preferred term for each treatment group. The summaries will present the number and percentage of participants using each medication by treatment group and overall. Participants may have more than one medication per drug class or preferred term. At each level of summarization, a participant is counted once if he/she reported one or more medications at that level. No statistical hypothesis tests will be performed.

5.9.7. Compliance

Compliance will be calculated and summarized by treatment group. Compliance will be calculated as $100 \times (\text{total number of capsules taken} / \text{total number of capsules expected to be taken})$. The total number of capsules taken is recorded on the eCRF. The number of expected capsules taken will be calculated as the duration of dosing (last dose date minus first dose date, plus 1) multiplied by 12. For example, if a participant is dosed for 10 days the expected number of capsules taken is 120.

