Hospital discharge readiness assessment		X	X	X	X	X	X		Refer to Section 8.1.5
Clinical status 6-point ordinal scale	X	X	X	X	X	X	X		Refer to Section 8.1.2
State of consciousness	X	X	X	X	X	X	X		Level of consciousness: alert (A), arousable only to voice (V), or pain (P) and unresponsive (U)

Procedure	Screening	Treatment Period			Follow-up			Post-study visit	Notes
		BL	Daily visits [‡]	EOT/ET*			EOS		
Study Day	-3 to -1	1	2-9	10	14	21	28	+60 days from EOS	Baseline (BL); End of Treatment (EOT), Early termination (ET); End of study (EOS) [‡] If a subject is discharged prior to Day 10, they will complete Day 5 and Day 10 visits assessments * This visit will be conducted at hospital discharge, if subject is discharged prior to Day 10
Visit window (days)				±1	±2	±2	±2	±10	
Randomization		X							
Study drug administration		X	X	X					Treatment to be administered during hospitalization only
Study drug accountability			X	X					
AE and SAE review		X	X	X	X	X	X		Adverse event (AEs), Serious AE (SAEs)
Prior and concomitant medication	X	X	X	X	X	X	X		
Survival status					X	X	X	X	

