6. STUDY DRUG

6.1. Study Drugs Administered

For more details on specific indications refer to the BLD-2660 Investigator Brochure (IB).

Table 3: Study Drug Administered

	Active	Control
Drug Name	BLD-2660	Placebo
Type	Drug (small molecule)	Drug
Dose Formulation	Capsules, Hard gelatin size '00'	Capsules, Hard gelatin size '00'
Unit Dose Strength(s)	150 mg	NA
Dosage Level(s)	900 mg BID (6 capsules BID) for a total of 1800 mg per day	NA
Route of Administration	Oral (PO); naso-gastric tube (NGT) may be used in special cases as detailed in Administration instruction below.	
Administration instruction	
Study drug to be taken orally BID:
 
 • Morning dose to be taken at least one hour before food • Evening dose to be taken at least 2 hours after food 
In the case where a subject needs mechanical ventilation, study drug can be administered via an NGT by opening the study drug capsules and suspending the contents in the required amount of water as described in the Pharmacy Manual, then administering through the tube. Lavage with additional 20-30 mL of water to ensure study drug does not stick to the tubing. Do not attempt to administer through a feeding tube.
	
Sourcing	Study drug will be provided to the site centrally by the Sponsor or designated representative.	
Packaging and Labeling	Drug product, both active and placebo, will be supplied in bulk packaging (40 capsules/bottle). Label text will at a minimum include the protocol number, lot number, storage conditions, and Sponsor name and address. Labels comply with regulatory requirements for study drugs.	

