where $z_{\alpha/2}$ and z_{β} are the value from a standard normal distribution, π is the proportion of participants randomized to control, $1 - \pi$ is the proportion of participants randomized to active and θ is the standardized effect size we wish to detect. For this study $\alpha = 5\%$, $\beta=10\%$, $\pi=1/3$ and $\theta=0.625$ (i.e., $25/40$).

4. Analysis Sets

For purposes of analysis, the following populations are defined:

Population	Description
Enrolled	All randomized participants
Full Analysis Set (FAS)	All randomized participants who receive at least one dose of study drug. This population will be used for all efficacy analyses
Modified Intent to Treat (MITT)	All randomized participants who receive at least one dose of study drug and one post baseline assessment of the SpO ₂ /FiO ₂ ratio. This population will be used for the primary and secondary endpoints related to improvement in SpO ₂ /FiO ₂ ratio.
Per Protocol Analysis Set (PP)	All randomized participants who receive at least 6 doses of study drug without any major protocol violations that would impact the assessment of the primary efficacy endpoints. This population will be used for efficacy analyses of the primary efficacy endpoints
Safety Analysis Set	All enrolled participants who receive any study drug
PK Analysis Set	All enrolled participants who receive any study drug and have plasma concentration data

5. Statistical Analyses

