5.4. Participant Disposition

A clear accounting of disposition, including the numbers and percentages of participants screened, randomized, completed treatment and completed post treatment follow-up and completed post study follow-up, will be reported overall and by treatment group. In addition, the primary reasons for early discontinuation of study intervention during the treatment period and early study discontinuation will be reported overall and by treatment group. A graphical representation of participant disposition, by treatment group, will be produced using a CONSORT flow diagram.

A summary of the number of participants included in each analysis set (i.e., FAS, MITT, PP, Safety, PK) will be provided overall and by treatment group. Participants could be excluded from an analysis set for more than one reason. All participants excluded from an analysis set will be listed with the reason(s) for exclusion.

A tabular summary of all major protocol violations will be provided by treatment group and overall. Major protocol violations will be classified as follows:

- Violations of inclusion and exclusion criteria
- Receiving the wrong study intervention
- Non-compliance with study intervention. A participant is defined as non-compliant if the participant took < 80% of the study intervention.
- Taking a prohibited medication
- Other

As participants can report multiple protocol violations, they will be included for each observed violation (i.e., these categories will not be mutually exclusive).

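### The SAP compliance formula counts one-dose days as full days and ends at the last dose taken, so it can mislabel some short courses and cannot register early stopping

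*SAP*

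**What the plan says.** SAP 5.9.7 defines compliance as capsules taken over capsules expected, as a percentage. The expected number is "the duration of dosing (last dose date minus first dose date, plus 1) multiplied by 12", with the example that "if a participant is dosed for 10 days the expected number of capsules taken is 120". There is no rule for a first or last day with a single dose.

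The regimen is "900 mg BID (6 capsules BID) for a total of 1800 mg per day" (Protocol 6.1, Table 3). Treatment runs "over 10 days (through Day 10/end of treatment) or until hospital discharge, if sooner" (SAP 1.2), and the Schedule of Activities adds: "Treatment to be administered during hospitalization only".

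SAP 5.4 lists non-compliance among the major protocol violations: "A participant is defined as non-compliant if the participant took < 80% of the study intervention". It does not name the denominator or cite 5.9.7, but 5.9.7 holds the only compliance formula in the SAP. The PP set in SAP section 4 takes randomised participants "who receive at least 6 doses of study drug without any major protocol violations", and the sentence goes on to limit this to violations that would affect assessment of the primary endpoints. SAP 5.5.3 repeats both primary analyses in the PP set. For time to clinical improvement this is the only sensitivity analysis listed.

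**The concern.** Dosing is twice daily, starts on the day of randomisation and ends at discharge. A patient can therefore start with an evening dose, or go home after a morning dose, without missing anything. The formula still expects 12 capsules on such a day, and on a short course that shortfall alone can bring the score under 80%.

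The opposite problem lies at the other end. The denominator closes on the date of the last dose actually taken, so doses forgone after early stopping are never counted as expected.

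At stake are the compliance summary, the major-violation table and, through it, possibly who is in the PP set. Short courses are foreseen. SAP 5.8.1 tabulates exposure from 0-3 days upward, and SAP 5.5.2 adds Days 6 to 9 to the repeated-measures model only if most participants are not discharged before Day 10.

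**Working it through.** **Inputs.** 6 capsules per dose and 2 doses per day (Protocol 6.1); expected capsules = 12 per calendar day from first to last dose (SAP 5.9.7); violation if below 80% (SAP 5.4); PP minimum of 6 doses (SAP section 4). I assume that the 80% rule uses the 5.9.7 formula.

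**The plan's own example.** (10 − 1 + 1) × 12 = 120 capsules for 10 days. This agrees.

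**General form.** Let D be the calendar days from first to last dose, m the number of one-dose end days (0, 1 or 2), and x the due doses missed in between.

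- SAP score = 100 × 6(2D − m − x) / (12D) = 100 × (2D − m − x) / (2D)
- Share of due doses taken = 100 × (2D − m − x) / (2D − m)

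The SAP score is below 80% when m + x > 0.4D.

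**No dose missed (x = 0, so the true share is 100%).**

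| D | m = 2: doses, score | m = 1: doses, score |
|---|---|---|
| 1 | not possible | 1, 50.0% (flagged) |
| 2 | 2, 50.0% (flagged) | 3, 75.0% (flagged) |
| 3 | 4, 66.7% (flagged) | 5, 83.3% |
| 4 | 6, 75.0% (flagged) | 7, 87.5% |
| 5 | 8, 80.0% (not below 80%) | 9, 90.0% |
| 6 | 10, 83.3% | 11, 91.7% |
| 10 | 18, 90.0% | 19, 95.0% |

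With m = 0 the score is 100% at any D. Of the flagged rows, only the 4-day course with 6 doses (36/48 = 75%) reaches the PP minimum.

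**One dose missed (x = 1).**

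| D | m | Taken / due | True share | SAP score |
|---|---|---|---|---|
| 4 | 1 | 6 / 7 | 85.7% | 6/8 = 75.0% |
| 5 | 2 | 7 / 8 | 87.5% | 7/10 = 70.0% |
| 6 | 2 | 9 / 10 | 90.0% | 9/12 = 75.0% |
| 7 | 2 | 11 / 12 | 91.7% | 11/14 = 78.6% |

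All four have at least 6 doses and a true share above 80%, and all four are flagged.

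**Early stopping.** After k full days with nothing missed, the score is 12k/12k = 100% for any k. For k = 3 it is 36/36 = 100%. That is 6 doses, which meets the PP minimum, and 36/120 = 30% of a full 10-day course.

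**If 5.4 instead means the planned 120 capsules.** Seven full days followed by discharge gives 84/120 = 70%, a violation produced by recovery. Section 5.4 needs a stated denominator on either reading.

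**The case against.** The strongest reply is that little depends on this. Both primary analyses use the FAS (SAP 5.5.2). The 6-dose minimum already keeps the 2-day and 3-day patterns out of the PP set, along with anyone who stops after 2 full days (4 doses). PP exclusion also requires a violation that would affect the primary endpoints, so a patient flagged only by day-counting need not be removed. All of this stands and limits the reach. It does not cover the 4-day, 6-dose course, the one-missed-dose courses above, or the patient who stops after 3 full days.

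A second reply is that adherence while on drug and persistence on drug are separate quantities. SAP 5.8.1 already summarises exposure duration, and SAP 5.4 reports reasons for early discontinuation. That is a fair design choice, and early stopping is therefore not hidden from the report. What remains unstated is whether stopping early in hospital counts as a violation for the PP set.

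Third, running the denominator simply to discharge or Day 10 would create new false violators. A fully adherent patient who dies in hospital after 5 full days would score 60/120 = 50%, and Protocol 7.2 lists adverse events and physician decision among the accepted reasons for stopping drug. This is correct, and the fix below allows for it.

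A reader might infer that adherent short-stay patients in general become violators, or that everyone who quits early scores 100%. The documents support neither. The first needs 4 calendar days or fewer with two one-dose end days, or 2 or fewer with one, if nothing is missed. The second needs full days and no missed dose; a stopper with one-dose end days loses the same share as an adherent patient (75% over 4 days with two).

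**Conclusion.** The point holds as a minor error in a stated rule. The formula gives the wrong score whenever an end day has one dose. It crosses the 80% limit wrongly for no-miss courses of up to 4 days with two such days (up to 2 days with one), and for one-miss courses of up to 7 days with two. It also gives 100% to a patient who takes 3 full days and stops while still hospitalised.

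The consequences are confined to the compliance summary, the violation table and possibly the PP sensitivity analyses. No primary estimate or p-value changes. It would also go too far to infer that the falsely flagged patients are mainly early discharges: the documents give no frequency for evening starts or morning last doses.

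The conclusion rests on two assumptions: that the 80% rule in SAP 5.4 uses the 5.9.7 formula, which is the natural reading but is not stated, and that one-dose days occur, which the dosing rules permit.

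**What to change.** - In SAP 5.9.7, define expected capsules as 6 × the number of doses due from the actual first dose to the earliest of hospital discharge, Day 10, death or documented permanent discontinuation. A one-dose first or last day then counts as 6 capsules.
- Use dose times or morning/evening records if these were captured. For the eCRF, Protocol 6.5 names start, stop and delay dates but not times. If times are missing, state a first-day and last-day convention.
- In SAP 5.4, cite this definition in the 80% rule.
- Report premature discontinuation while hospitalised separately, and state whether it counts as a violation relevant to the PP set. This is needed because the corrected denominator still ends at documented discontinuation.

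The cost is SAP wording and a small programming change, with no new visits or procedures. Enrolment is already complete (SAP 5.10), so the dose-level count depends on per-dose data already being available.
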